### 16.5 Appendix V: Retigabine Muscle Cramp Diary – Visual Analog Scale (Pain Scale)

	Scale	
No pain	0	
	1	
Mild, annoying pain	2	
	3	
Nagging, uncomfortable, troublesome pain	4	
	5	
Distressing, miserable pain	6	
	7	
Intense, dreadful, horrible pain	8	
	9	
Worst possible, unbearable, excruciating pain	10	

## 16.6 Appendix VI: Edinburgh Handedness Inventory- Short Form

### Edinburgh Handedness Inventory - Short Form

Please indicate your preferences in the use of hands in the following activities or objects:

	Always right	Usually right	Both equally	Usually left	Always left
Writing					
Throwing					
Toothbrush					
Spoon					

#### Scoring:

For each item: Always right = 100; Usually right = 50; Both equally = 0; Usually left = -50; Always left = -100

To calculate the Laterality Quotient add the scores for the four items in the scale and divide this by four:

Writing score	
Throwing score	
Toothbrush score	
Spoon score	
Total	
Total ÷ 4 (Laterality Quotient)	

Classification:	Laterality Quotient score:
Left handers	-100 to -61
Mixed handers	-60 to 60
Right handers	61 to 100

**SAP REVISION HISTORY**

Version	Date	Description of Changes
1.0	27 Sep 2018	Initial version

## 1. Introduction

This Statistical Analysis Plan (SAP) defines the outcome measures and analysis samples and specifies the planned analyses of data from [name] Ezogabine trial. This SAP is specific to analysis of data related to the ALS participants in the randomized intervention trial. The SAP supplements the clinical protocol. Please refer to the clinical protocol for details on the rationale for the intervention, eligibility criteria, conduct of the trial, clinical assessments and the timing of their use in the trial, definitions and reporting of adverse events, data management conventions, and regulatory oversight and compliance procedures. In case of discrepancies between the SAP and the clinical protocol concerning matters of analysis, the SAP is authoritative. On all other matters, the clinical protocol is authoritative.

## 2. Study Design

### 2.1 Overview

This is a multicenter, double-blind, placebo-controlled, three-arm, parallel-group, phase 2 randomized controlled trial to examine the effect of two dosages of ezogabine on neuronal excitability in ALS patients. The trial also enrolls unmatched and age-matched healthy control subjects to evaluate disease-dependent differences in baseline measures and longitudinal changes in neuronal excitability. Trial participation for ALS participants includes a screening visit, randomization to 600 mg/day or 900 mg/day ezogabine or placebo, 10 weeks of follow-up on study drug, and 4 weeks of follow-up after last dose of study drug. Trial participation for unmatched healthy control (UHC) participants includes a screening visit and up to 4 additional neurophysiological testing visits with one or two neurophysiologists over a span of up to 6 weeks. Trial participation for age-matched healthy control (MHC) participants includes a screening visit and two follow-up visits over 12 weeks. The trial is registered at Clinicaltrials.gov as study NCT02450552 (see <https://clinicaltrials.gov/ct2/show/NCT02450552>).

### 2.2 Study Objectives

The primary efficacy objective of the trial is to determine whether ezogabine reduces neurophysiological excitability indices in ALS participants as assessed by transcranial magnetic stimulation (TMS) and threshold tracking axonal nerve conduction studies (TTNCS). Secondary efficacy objectives include evaluating the effect of ezogabine on measures of clinical progression, including functional scores, vital capacity, and muscle strength, and on measures of muscle cramping and fasciculations.

The safety objectives of the trial are to assess the safety and tolerability of ezogabine by assessing treatment-emergent adverse events (TEAEs), vital signs, laboratory assessments, electrocardiography (ECG), urologic symptoms, ophthalmologic symptoms, and suicidality.

### 2.3 Study Populations

Individuals eligible for trial participation as an ALS participant are men or women at least 18 years old who meet the El Escorial criteria of possible, laboratory-supported probable, probable, or definite criteria for a diagnosis of ALS and have a slow vital capacity (SVC) at least 50% of that expected based on age, sex, and height. Individuals eligible for study participation as an UHC participant are men or women at least 18 years old who do not have a history or family

history of possible motor neuron disease. Individuals eligible for study participation as a MHC participant are men or women who do not have a history or family history of possible motor neuron disease and are within 10 years of age of an enrolled ALS participant. Detailed inclusion and exclusion criteria are specified in the clinical protocol.

Participants will be recruited from a total of 12 clinical sites located through the US.

## **2.4 Participant Flow and Site Approval**

After providing informed consent, approximately 5 UHC participants will be screened for eligibility at each site, including assessment of neurophysiology by TMS and TTNCS by one or two neurophysiologists. Each UHC participant will have up to 4 additional neurophysiological testing visits over a span of up to 6 weeks.

After completing TMS and TTNCS assessments of the first UHC participant, sites must receive approval from the Coordination Center before continuing enrollment of UHC participants. Approval will be based on review of TMS and TTNCS data by the respective central reading centers. After completing enrollment of approximately 5 UHC participants, sites must receive approval from the Coordination Center before initiating recruitment of ALS participants.

After a site is activated for recruitment of ALS participants and after each ALS patient provides informed consent and is determined eligible, approximately 120 ALS participants will be randomized to receive ezogabine 600 mg/day, ezogabine 900 mg/day, or placebo in a 1:1:1 ratio, stratified by clinical site. The first dose of study drug is administered at the baseline visit. ALS participants are exposed to study drug for 10 weeks, from baseline to a week 10 telephone call. ALS participants complete in-clinic evaluations at weeks 4, 6, 8, and 12 and complete follow-up by telephone at weeks 2, 10, and 14 to assess for TEAEs and update concomitant medication logs. Participants who discontinue study drug should remain on study following the normal schedule of assessments. Patients withdrawing consent are asked to delay withdrawing consent until after they return for a Final Safety Visit approximately 2 weeks after their last dose of study drug and after they complete a final telephone call 4 weeks after their last dose of study drug.

Detailed descriptions of study procedures and timing are specified in the clinical protocol.

## **2.5 Treatment Allocation**

Prior to the baseline visit, eligible ALS participants are randomly allocated in equal proportions to one of three treatment groups, ezogabine 600 mg/day, ezogabine 900 mg/day, or placebo, according to a permuted-block randomization schedule, stratified by site. The randomization schedule was prepared by computer program by the unblinded study statistician.

## **2.6 Treatment Administration**

Study drug will be orally self-administered in film-coated immediate-release tablets of a variety of strengths of ezogabine or matching placebo. In the 600 mg/day arm, ezogabine is titrated as follows: 100 mg TID for week 1, 150 mg TID for week 2, 200 mg TID for weeks 3 through 8, 200 mg BID for week 9, and 200 mg QD for week 10. In the 900 mg/day arm, ezogabine is titrated as follows: 100 mg TID for week 1, 150 mg TID for week 2, 200 mg TID for week 3, 250 mg TID for week 4, 300 mg TID for weeks 5 through 8, 200 mg BID for week 9, and 200 mg QD for week 10. In the placebo arm, participants receive a matching pseudo-titration of placebo tablets matched for size, color, and presentation.

## 2.7 Allocation Concealment

The randomization schedule is known only by the unblinded study statistician who generated the schedule and by the study drug distributor. Concealment of the true treatment allocation of specific participants is achieved by use of anonymous subject identifiers to link participants with specific study drug kits and by use of matching active and placebo tablets and titration schedules. Clinical members of the Steering Committee, site investigators and other site staff, clinical coordination and data management staff, the medical monitor, and all participants are blinded to participant treatment allocations. The Data and Safety Monitoring Board (DSMB) members are provided treatment-specific information in order to monitor the trial but such information is masked by use of coded values to identify the treatment groups. The DSMB may request the true treatment identities.

## 2.8 Schedule of Assessments for ALS Participants

Activity	Screening	Baseline 	Week 2	Week 4 	Week 6 	Week 8 	Week 10	Week 12	Week 14
	CLINIC	CLINIC	CALL	CLINIC	CLINIC	CLINIC	CALL	CLINIC	CALL
	Day -21 to -1	Day 0	Day 14 ± 3	Day 28 ± 3	Day 42 ± 3	Day 56 ± 3	Day 70 ± 3	Day 84 ± 3	Day 98 +5
Written Informed Consent	X								
Inclusion/Exclusion Review	X								
Medical History	X								
Demographics	X								
ALS Diagnosis History	X								
Concomitant Medication Review	X	X	X	X	X	X	X	X	X
Adverse Event Review 	X	X	X	X	X	X	X	X	X
Physical Examination	X								X
Neurological Exam	X								X
Manual Muscle Testing (MMT)	X								X
Vital Signs 	X	X		X	X	X			X
12-Lead Electrocardiogram (ECG)	X	X 			X				X
Height & Weight 	X	X		X	X	X			X
Safety Labs 	X			X	X	X			X
Urological Symptom Score	X			X		X			X
ALSFRS-R	X	X		X	X	X			X
Slow Vital Capacity (SVC)	X	X		X	X	X			X
Hand Held Dynamometry (APB only)	X	X		X	X	X			X
Assign Global Unique Identifier (GUID)	X								
Blindedness Questionnaire and Exit Survey									X
Suicide Assessment (C-SSRS)		X		X	X	X			X
Edinburgh Handedness Inventory – short form	X								
Blood collection for iPSC Lines				X 	(X  )	(X  )			
Neurophysiological Testing (TMS/NCS)	X	X		(X  )	X	X			(X  )
Ophthalmologic Examination 		X							X
Lumbar Puncture (Optional)					X 				
Pharmacokinetics (PK)/Biobanking					X				

Activity	Screening CLINIC	Baseline  CLINIC	Week 2 CALL	Week 4  CLINIC	Week 6  CLINIC	Week 8  CLINIC	Week 10 CALL	Week 12 CLINIC	Week 14 CALL
	Day -21 to -1	Day 0	Day 14 ± 3	Day 28 ± 3	Day 42 ± 3	Day 56 ± 3	Day 70 ± 3	Day 84 ± 3	Day 98 ± 5
Telephone Call 			X				X		X
Randomization 		X							
Administer/Dispense Study Drug		X 		X					
Drug Accountability/ Compliance		X		X 	X 	X 		X 	
Review of Muscle Symptoms Diary 		X		X	X	X		X	
Fasciculation Assessment Form		X		X	X	X		X	

 All clinic visits after the Baseline Visit and before Week 14 will have a ± 3 day window.

 Screening procedures must be completed prior to the Baseline Visit, which will be scheduled up to 21 days after the Screening Visit.

 Study staff should document the time the last dose of ezogabine was administered.

Adverse events that occur AFTER signing the informed consent form will be recorded.

 Vital signs include systolic and diastolic pressure in mm Hg, respiratory rate/minute, heart rate/minute and temperature.

 Height measured at Screening Visit only.

 Labs include Hematology (CBC with differential), Complete Chemistry Panel, Liver Function Tests, Urinalysis and serum pregnancy test (WOCBP, screening visit only).

 Blood for iPSC lines can be collected at either week 4, 6 or 8.

 Ophthalmologic Examinations may be scheduled separately, but within 14 days prior to Baseline Visit and within 14 days of Week 12 Visit.

 Subjects will be called at the designated time points, as a reminder to escalate up or taper off study drug, when appropriate.

 Randomization should occur at or prior to the Baseline Visit.

 Administer first dose of study drug AFTER all Baseline Visit procedures are completed (with the exception of ECG testing). Subjects to take study drug until the Week 10 call.

 Review dosing diary

 Muscle symptoms will be completed every day, starting at the Baseline visit, with a Muscle Symptom Diary and should be reviewed by study staff at every visit after Baseline.

 ECG testing should be performed 3 hours post initial study drug administration.

 Lumbar puncture is optional

 Only participant enrolled prior to protocol version 4 were scheduled to complete TMS and TTNCS testing at the week 4 and 12 visits.

### 3. Statistical Methodology

#### 3.1 General Considerations

##### 3.1.1 Statistical Software

All statistical analyses will be performed using SAS (SAS Institute, NC, USA) or R (R Foundation for Statistical Computing, Vienna, Austria).

##### 3.1.2 Summary Statistics

Data will be summarized with respect to disposition, demographics, pre-treatment characteristics, safety outcomes, tolerability, and efficacy outcomes. Summary statistics for continuous variables will include the number of subjects, the mean, median, standard deviation, and range. For categorical data, summaries will include counts and percentages.

### 3.1.3 Precision

Results will generally be reported to 3 significant figures. Percentages will generally be reported to 0.1 percentage points. P-values will be reported to two digits when greater than or equal to 0.095, to three digits when greater than or equal to 0.00095 and less than 0.095, and as <0.001 for all smaller values.

## 3.2 Study Endpoints

### 3.2.1 Efficacy Endpoints

The primary efficacy endpoint is the change from pre-treatment to the average of the week 6 and week 8 visits in paired-pulse short-interval intracortical inhibition (SICI) assessed by TMS.

The key secondary efficacy endpoint is the change from pre-treatment to the average of the week 6 and week 8 visits in resting motor evoked potential (MEP) threshold (RMT) assessed by TMS.

The other secondary efficacy endpoints are the change from pre-treatment to the average of the week 6 and week 8 visits in the following measures.

TMS measures:

- MEP amplitude at 120% of RMT,
- Intracortical facilitation (ICF), and
- Cortical silent period (CSP).

TTNCS measures:

- Strength duration time-constant (SDTC),
- Depolarizing and hyperpolarizing electrotonus at 90 to 100 ms (TEd(90-100 ms) and TEh(90-100 ms)),
- Recovery cycle measures of relative refractory period (RRP), superexcitability, and subexcitability, and
- Compound motor action potential (CMAP).

Clinical measures:

- ALS Functional Rating Scale-Revised (ALSFRS-R) total score,
- Slow vital capacity (SVC),
- Abductor pollicis brevis (APB) muscle strength by hand-held dynamometry (HHD),
- Muscle cramping frequency and pain, and
- Fasciculation occurrence and interference with daily life.

Exploratory efficacy measures include: maximum amplitude, minimum amplitude, midpoint of activation, and slope at the midpoint of activation from input/output curves; rheobase, TEd(40-60 ms), TEh(10-20 ms), TEd(peak), subexcitability after second pre-pulse, and stimulus for 50% maximum response assessed by TTNCS; MEP amplitude at 120% of RMT divided by CMAP.

### 3.2.2 Safety Endpoints

The following safety endpoints will be evaluated:

- Proportion of participants experiencing and number of unique events of each type of TEAE and serious TEAE classified by MedDRA system organ class and preferred term,
- Proportion of participants experiencing and number of unique events of TEAEs classified by seriousness, severity, relatedness to study drug, relatedness to TMS and TTNCS procedures, action taken with study drug, action taken with TMS/TTNCS, and outcome, summarized across all MedDRA terms,
- Instances of treatment-emergent laboratory abnormalities classified by assay, whether the abnormality is below or above the normal range, and extend of deviation from normal,
- Mean change from baseline in weight
- Proportion of participants experiencing treatment-emergent clinically significant ECG abnormalities
- Proportion of participants experiencing treatment-emergent ophthalmologic complication,
- Mean change in AUA Symptom Score and proportion of participants with mild, moderate, or severe symptoms by visit,
- Proportion of participants reporting any treatment-emergent suicidal ideation
- Maximum post-baseline suicidal ideation planning, frequency, duration, controllability, deterrents, and reasons
- Proportion of participants reporting any post-baseline suicidal behavior, actual attempts, non-suicidal self-injurious behavior, interrupted attempts, aborted attempts, preparatory acts or behaviors, or completed suicide
- Maximum post-baseline suicidal behavior lethality and potential lethality

Reported proportions will use as their denominator all participants in the Safety and Tolerability sample (see Section 3.5 below).

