## 2.2 Rationale

The overarching rationale for the proposal is that motor neuron hyperexcitability contributes to neurodegeneration in ALS and that reduction of neuronal hyperactivity may slow the disease course. The clinical neurophysiological techniques used to demonstrate hyperexcitability may be useful as biomarkers to indicate reduction in excitability with treatment. Studies involving clinical neurophysiology, mouse motor neuron models and human iPSC-derived motor neurons from ALS patients all suggest that motor neuron hyperexcitability may contribute to motor neuron death in ALS. In particular, *in vitro* treatment of ALS patient-derived motor neurons with ezogabine can reverse the hyperexcitability and improve motor neuron survival. On account of these data, the primary goal of this study is to determine whether ezogabine treatment safely reduces neurophysiological indices of motor neuron hyperexcitability in ALS subjects.

The upper dose limit for this study was chosen based on tolerability in previous epilepsy studies (Porter et al, 2007; Brodie et al, 2010; French et al, 2011). Oral doses of 600 mg/day (all doses divided TID), 900 mg/day, and 1200 mg/day were used in two of the three studies. At 1200 mg/day, subject drop out due to AEs was nearly 30% (vs. 20% in the 900 mg/day dose) in Porter et al. (2007). On the opposite end, there was no statistically significant benefit in the 600 mg/day dose compared to placebo, while a clear reduction in seizure frequency was observed with 900 and 1200 mg/day treatments. There is no indication, given the stable linear PK properties over multiple doses and lack of drug-drug interactions in repeated studies, that pharmacokinetics or tolerability would differ markedly in ALS subjects (no CYP metabolism; predominantly renal clearance). We thus chose a fixed dosing strategy with 600 mg/day and 900 mg/day arms to include two doses that were both likely to be tolerated and likely to reduce excitability. Importantly, we will determine whether the CSF concentration approaches the known EC50 of ~ 2  $\mu$ M from both our *in vitro* studies and heterologous expression of Kv7 channels (Wickenden et al., 2000). CSF levels were not measured in the epilepsy studies. With regard to study duration, the observed effects on hyperexcitability in the most relevant clinical studies (Caramia et al.,

2000; Stefan et al., 2001) were observed within the time frame (4 weeks of maintenance dose treatment) proposed in the study.

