## 3.5 Analysis Samples

The following analysis samples will be used for testing safety, tolerability, and efficacy endpoints:

- Safety and Tolerability (ST) Sample: ALS participants who are eligible, randomized, and take at least one dose of study drug, classified according to the actual treatment received. Observations made after premature permanent discontinuation of study drug are included in this sample, should such participants remain on study.
- Efficacy Modified Intent-to-treat (mITT) Sample: ALS participants who are eligible, randomized, and take at least one dose of study drug, classified according to their randomized treatment assignment. Observations made after premature permanent discontinuation of study drug are included in this sample, should such participants remain on study.
- Efficacy Per-protocol (PP) Sample: ALS participants who are eligible, randomized, and take at least one dose of study drug, classified according to the actual treatment received. Observations made after premature permanent discontinuation of study drug (whether due to intolerance, early termination, loss to follow-up, or death) are excluded from this sample.

- Efficacy Low RMT (loRMT) Sample: ALS participants and observations in the PP sample with RMT less than 67% of maximum stimulator output. This criterion ensures that the full TMS input/output curve could be conducted.
- Efficacy All Quality (AllQual) Sample: ALS participants and observations in the PP sample with no restriction that TMS quality is good.

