### 3.9.3 Safety Labs

The absolute level and the absolute change from baseline for each safety laboratory assay will be summarized as means, standard deviations, medians, and ranges at each visit by treatment group. The proportion of participants with safety lab levels below the lower limit of normal or above the upper limit of normal will be summarized by treatment group by visit and at any post-baseline visit.

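### SAP 3.2.2 divides examination-based safety proportions by the whole Safety and Tolerability sample, so missed assessments shrink the reported rates and by-visit AUA severity categories do not sum to 100%

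*SAP*

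**What the plan says.** SAP 3.2.2 lists the safety endpoints and then fixes one denominator for them: "Reported proportions will use as their denominator all participants in the Safety and Tolerability sample". SAP 3.5 defines that sample as "ALS participants who are eligible, randomized, and take at least one dose of study drug, classified according to the actual treatment received". Entry requires no post-baseline assessment.

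The list mixes two kinds of outcome. Treatment-emergent adverse events (TEAEs) can be reported at any contact. Others need an examination or questionnaire, for example "Mean change in AUA Symptom Score and proportion of participants with mild, moderate, or severe symptoms by visit" and "Proportion of participants experiencing treatment-emergent ophthalmologic complication", together with ECG abnormalities and the C-SSRS items.

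No other section makes an exception. SAP 3.9.2 (suicidality) names no denominator. SAP 3.9.3 says that the proportions of participants with out-of-range laboratory values "will be summarized by treatment group by visit and at any post-baseline visit", also without a denominator. SAP 3.8.6 deals with missing efficacy data only. SAP section 1 makes the SAP authoritative over the protocol on matters of analysis.

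**The concern.** A participant who was not assessed cannot contribute a finding, yet stays in the denominator. This has two consequences.

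- **AUA severity by visit.** The lowest category, mild, covers scores 0 through 7 (SAP 3.3.8), so there is no separate event-free class. A participant without the visit belongs to none of the three categories. All three percentages fall, and they cannot sum to 100%.
- **Any-time outcomes that need an examination.** On the normal schedule there is one post-baseline eye examination, at Week 12 (Protocol 8.7). A participant who has neither that examination nor one at the Final Safety Visit is in effect recorded as free of ophthalmologic complications. The same applies to anyone with no post-baseline C-SSRS, though four scheduled visits make that less likely.

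These outcomes matter here. Protocol 11.1.1.1 names urinary retention and retinal abnormality among the events of special interest, and Protocol 10.1.13 says the AUA score was included because of urinary risk. If assessments were also missed more often in one arm than another, the tables would misstate the contrast between arms.

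**Working it through.** **Inputs from the documents.** About 120 participants are randomized 1:1:1, hence 40 per arm. SAP 3.4 and Protocol 13.8 allow for up to 25% loss to follow-up. This is the only planned loss figure in either document. It was set for sample size and is not given by arm. Event rates and unequal missing shares below are assumptions.

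**The plan's own figure.** With difference 25, SD 30 and two-sided alpha 0.027, a two-sample t-test needs 29 evaluable per group for 80% power. Allowing for 25% loss, 29 / 0.75 = 38.7, so 39, against the stated 40. With 40 × 0.75 = 30 evaluable, power is 0.828. The stated sample size is reproduced, and 30 assessed of 40 is a fair planning case.

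**Effect of the rule.** Let N be the arm's size in the safety sample, n the number assessed, x the number with the finding, and m = 1 − n/N.

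Reported proportion = x/N = (x/n) × (1 − m).

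With 9 events among 30 assessed: 9/30 = 30.0%, but 9/40 = 22.5%, which is 30.0% × 0.75.

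**AUA by visit.** Suppose 30 assessed split 18 mild, 8 moderate, 4 severe:

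| | Mild | Moderate | Severe | Sum |
|---|---|---|---|---|
| Of 30 assessed | 60.0% | 26.7% | 13.3% | 100% |
| Of 40 (SAP rule) | 45% | 20% | 10% | 75% |

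The shortfall in the sum equals the share missing, whatever the risk among those not seen.

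**Comparison of arms.** Assume that those missing have the same risk as those assessed.

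| Assumed rate, active / placebo | Missing, active / placebo | Reported, active / placebo | Reported difference | True difference |
|---|---|---|---|---|
| 30% / 15% | 25% / 25% | 22.5% / 11.25% | 11.3 points | 15 points |
| 30% / 15% | 25% / 10% | 22.5% / 13.5% | 9.0 | 15 |
| 30% / 15% | 25% / 0% | 22.5% / 15% | 7.5 | 15 |
| 30% / 15% | 20% / 10% | 24% / 13.5% | 10.5 | 15 |
| 30% / 15% | 10% / 5% | 27% / 14.25% | 12.8 | 15 |
| 20% / 20% | 25% / 25% | 15% / 15% | 0 | 0 |
| 20% / 20% | 25% / 10% | 15% / 18% | −3 | 0 |
| 20% / 20% | 10% / 5% | 18% / 19% | −1 | 0 |

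Equal missingness creates no false difference but shrinks a true one. Unequal missingness can create a false one.

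**Which arm loses most.** If p_mis is the rate among those not assessed, the full-sample rate is (1 − m)(x/n) + m × p_mis, so the rule falls short by m × p_mis. In absolute points, 10% missing at a 30% rate loses 3.0 points, while 25% missing at a 10% rate loses 2.5. The arm with more missing data has the larger relative loss when risks are similar, but not always the larger absolute one.

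**The case against.** Much can be said for the plan, and several points stand.

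- **Follow-up is designed to continue.** SAP 2.4 keeps participants who stop drug on the normal visit schedule. Those withdrawing consent are asked to attend a Final Safety Visit that includes eye examination, ECG, laboratory tests, AUA and C-SSRS (Protocol 8.9). This reduces missingness without removing it. Attendance is requested, not assured. Deaths and losses to follow-up are not captured, one extra visit cannot fill several empty AUA visits, and Protocol 8.11 expects some procedures to be missed through illness or disability.
- **ECG is little affected.** A post-dose ECG is scheduled on Day 0, so almost nobody in the sample lacks one.
- **Adverse event reporting is a second route.** Visual and urinary events are reportable within 24 hours (Protocol 11.2.3), and clinically significant abnormal findings enter the TEAE tables.
- **The summaries are descriptive.** SAP 3.1.2 requires counts, and the number of subjects for continuous variables, so a careful reader could recover the number with an AUA score at a visit. Disposition and time to discontinuation are also reported by arm. This helps, but does not make the printed percentages right.
- **Assessed-only proportions can be biased too.** If missingness is related to health, the assessed are not representative. That is a reason to show the number missing.

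A reader might infer something stronger: that dropout in this trial is known to rise with dose, so the rule will make the higher dose look safer. The documents do not support this. Protocol 2.2 says of 1200 mg/day in one epilepsy study that "subject drop out due to AEs was nearly 30% (vs. 20% in the 900 mg/day dose" group). It gives no placebo or 600 mg/day figure, 1200 mg/day is not an arm here, and dropout due to adverse events is not the same as missing an assessment.

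**Conclusion.** The point holds as an error in a stated rule, confined to outcomes that need an assessment. AUA severity by visit is the clearest case: at any visit with missing data the categories sum to less than 100%, with no assumption about risk needed. The ophthalmologic endpoint is next, because so few examinations inform it. The C-SSRS items are affected less and the ECG endpoint hardly at all. The ST denominator for TEAE proportions is conventional and should stay.

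The relative understatement equals the share missing, so up to a quarter if the planning loss of 25% were reached. Any distortion between arms depends on missingness by arm, which the documents do not give. The 18% versus 15% result for placebo and active at an equal 20% rate is an illustration, not a forecast.

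Two further readings should be avoided. Missing participants are not counted as event-free for AUA; they vanish from every category. And the laboratory proportions are not clearly under this rule: SAP 3.2.2 lists laboratory abnormalities as instances, and the proportions appear only in 3.9.3, where the denominator is left open.

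**What to change.** Replace the denominator sentence in SAP 3.2.2 with a rule by type of endpoint:

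- **TEAE proportions:** all participants in the ST sample, as now.
- **By-visit proportions** (AUA severity): ST participants with that assessment at that visit.
- **Examination-based proportions over any post-baseline time** (ophthalmologic, C-SSRS, ECG): ST participants with at least one post-baseline assessment of that type. State that the Day 0 post-dose ECG counts, if that is intended.
- **All of these tables:** show the numbers assessed and missing by arm.

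State in SAP 3.9.3 that the laboratory proportions follow the same rule.

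The cost is a short SAP amendment and a changed denominator in the affected tables. No new data are needed, and the efficacy analysis is untouched. The small downside is that assessed-only figures remain open to bias if missingness is related to health; the missing counts let a reader judge how far that could matter.
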